## **3.6 DISCUSSION OF STUDY DESIGN**

### **3.6.1 Number of Subjects**

The study is designed to enroll enough subjects to ensure at least 261 evaluable subjects reach Month 6. Accounting for discontinuation, it is anticipated that up to approximately 351 randomized subjects may be required. An evaluable subject is one who has at least 1 sputum culture result at Baseline (Day 1) and for each month through Month 6.

### **3.6.2 Study Duration**

This study has an anticipated recruitment period of 18-24 months, with each subject receiving treatment in the study for up to 16 months (excluding Screening and observational follow-up). Subjects will remain in the study for up to 31 months, approximately 2.5 months for Screening plus up to 16 months in the randomized open-label treatment phase plus 12 months in the off-treatment phase.

### **3.6.3 Premature Termination of Study Site**

For reasonable cause, either an individual Investigator may terminate participation prematurely or Insmmed may terminate this study prematurely. Written notification of the termination to each affected investigational site is required. Some conditions that may warrant termination include the following:

- discovery of an unexpected, significant, or unacceptable risk to the subjects enrolled in the study
- failure of the Investigator to enter study subjects at an acceptable rate
- insufficient adherence to protocol requirements (e.g., noncompliance) by the subject and/or the study site
- decision on the part of the Sponsor to suspend or discontinue development of the drug
- decision by a regulatory authority or the Sponsor to stop the study at any time, where applicable

Protocol Amendment #3 version: 22 February 2016

*This protocol is solely for the purpose of communicating information about the investigational drug between Insmmed Incorporated and study personnel. Information is not to be reproduced, abstracted or used for sharing of information for any other purpose, whatsoever, except with the written permission of Insmmed Incorporated.*

In the event of study discontinuation, subjects will discontinue the investigational treatments. Refer to [Section 5.12.1](#) for follow-up procedures.

The Sponsor will notify the regulatory authorities in all countries where the study is being conducted regarding the reason for terminating the study.

### **3.6.4 Assignment to Study Drug**

Eligible subjects will be stratified at Screening according to smoking status (current smoker or not) and prior multi-drug regimen (on treatment or off treatment for at least 3 months) and then randomly assigned in a 2:1 ratio to treatment with either LAI (590 mg) QD plus multi-drug regimen or to multi-drug regimen alone, using an interactive web response system (IWRS). Treatment randomization codes will be generated using SAS®.

### **3.6.5 Data Monitoring Committee**

In order to ensure the safety of subjects enrolled in INS-212, Insmmed plans to implement a Data Monitoring Committee (DMC). The Committee will consist of experts outside of Insmmed who are not involved in the study conduct. The DMC will provide a centralized review function independent of Insmmed clinical team and all other individuals associated with the conduct of the study. The DMC will be comprised of at least two physicians with pulmonary expertise who are not investigators in the clinical study and a statistician who is experienced in the evaluation of safety data. Further details are provided in the DMC charter.

## **4 STUDY POPULATION**

To be eligible for enrollment, subjects must meet all of the following inclusion criteria and none of the following exclusion criteria.

Protocol Amendment #3 version: 22 February 2016

*This protocol is solely for the purpose of communicating information about the investigational drug between Insmmed Incorporated and study personnel. Information is not to be reproduced, abstracted or used for sharing of information for any other purpose, whatsoever, except with the written permission of Insmmed Incorporated.*

## 4.1 INCLUSION CRITERIA

To be eligible for enrollment, a prospective patient must meet all of the following criteria:

1. be male or female, 18 years or older (20 years or older in Japan)
2. be positive for MAC on culture as defined in inclusion criterion No. 4 while being treated with a multi-drug treatment regimen (at least 2 antibiotics) for a minimum duration of 6 consecutive months that is either ongoing or was stopped no more than 12 months before Screening (exceptions to multi-drug treatment regimen for 6 consecutive months include treatment with doses or frequencies below those recommended by guidelines and/or short interruptions of therapy, both occurring due to safety/tolerability issues)
3. be diagnosed with MAC NTM lung infection with evidence of underlying lung disease such as nodular bronchiectasis and/or fibrocavitary disease by chest radiography or chest computed tomography. High resolution CT (HRCT) scan is preferred, if available
4. have a MAC lung infection documented by at least 2 positive cultures (MAC or mixed infection with MAC as the dominant species), consisting of at least one obtained within 6 months prior to Screening and one positive culture at Screening (cultures to be at least 1 month apart). Cultures may be obtained from sputum or bronchoscopy.
5. have a MAC-positive sputum at Screening
6. be willing to adhere to multi-drug treatment regimen during the course of the study
7. be able to produce approximately 3 mL of sputum or be willing to undergo an induction that produces approximately 3 mL of sputum for mycobacteriology
8. female of child bearing potential agrees to practice an acceptable method of birth control (e.g., true abstinence [refraining from heterosexual intercourse during the entire study], hormonal or barrier methods, partner sterilization, or intrauterine device [IUD]) while participating in the trial. Periodic abstinence (e.g., calendar, ovulation, symptothermal, post-ovulation methods), declaration of abstinence for the duration of the study, and withdrawal are not acceptable methods of contraception.

Protocol Amendment #3 version: 22 February 2016

*This protocol is solely for the purpose of communicating information about the investigational drug between Insmmed Incorporated and study personnel. Information is not to be reproduced, abstracted or used for sharing of information for any other purpose, whatsoever, except with the written permission of Insmmed Incorporated.*

9. the patient will provide written informed consent before performing any study related procedure
10. be willing to have serum specimens stored
11. be able to comply with study drug use, study visits, and study procedures as determined by the investigator.

#### **4.2 EXCLUSION CRITERIA**

A prospective patient with any of the following conditions must be excluded from this study:

1. patients with cystic fibrosis
2. patients whose MAC NTM infection is resistant to amikacin (as identified by MIC susceptibility  $>64 \mu\text{g/mL}$ )
3. patients who are not able to perform the 6MWT
4. positive pregnancy test or lactation at Screening. All women of child bearing potential will be tested. Women not of child bearing potential are defined as postmenopausal (i.e., amenorrheic for at least 1 year), or surgically or naturally sterile.
5. active pulmonary malignancy (primary or metastatic) or any malignancy requiring chemotherapy or radiation therapy within 1 year before Screening or anticipated during the study period
6. active allergic bronchopulmonary mycosis or any other condition requiring chronic systemic corticosteroids at a dose greater than the equivalent of 10 mg/day of prednisone within 3 months before Screening
7. active pulmonary tuberculosis requiring treatment at Screening
8. history of lung transplantation
9. initiation of chronic therapy (e.g., high dose ibuprofen, inhaled anti-inflammatory agents including steroids, low dose maintenance steroids, rhDNase) within 28 days before Day 1
10. administration of any investigational drug within 8 weeks before Screening

Protocol Amendment #3 version: 22 February 2016

*This protocol is solely for the purpose of communicating information about the investigational drug between Insmmed Incorporated and study personnel. Information is not to be reproduced, abstracted or used for sharing of information for any other purpose, whatsoever, except with the written permission of Insmmed Incorporated.*

11. prior exposure to LAI (including clinical study)
12. known hypersensitivity to aminoglycosides
13. use of inhaled or systemic aminoglycosides with activity against MAC (e.g., amikacin, kanamycin, or streptomycin) within 28 days before Day 1
14. acquired and primary immunodeficiency syndromes (e.g. HIV-positive patients regardless of CD4 counts)
15. significant (as determined by the investigator) hearing loss, vestibular dysfunction, neuromuscular weakness or a diagnosis of myasthenia gravis, where the potential risk of aminoglycoside toxicity outweighs the potential benefit
16. aspartate aminotransferase or alanine aminotransferase  $\geq 3$  times the upper limit of normal (ULN) or total bilirubin  $\geq 2$  times ULN at Screening
17. absolute neutrophil count  $\leq 500/\mu\text{L}$  at Screening
18. serum creatinine  $>2$  times ULN at Screening
19. current alcohol, medication or illicit drug abuse
20. any condition that, in the opinion of the Investigator, interferes with ability to safely complete the study or adhere to study requirements.
21. persons who have been committed to an institution by virtue of an order issued either by the judicial or the administrative authorities
22. in the opinion of the Investigator, patients who are not expected to survive the duration of the study
23. Patients with disseminated MAC infection

Protocol Amendment #3 version: 22 February 2016

*This protocol is solely for the purpose of communicating information about the investigational drug between Insmmed Incorporated and study personnel. Information is not to be reproduced, abstracted or used for sharing of information for any other purpose, whatsoever, except with the written permission of Insmmed Incorporated.*

### 4.3 REMOVAL OF SUBJECTS

A subject may be withdrawn from the study for any of the following reasons:

1. the event of the subject's death
2. the subject experiences an AE and the Investigator or the patient determines that withdrawal from the study is appropriate
3. a major protocol deviation that interferes with the integrity of the study data for this subject
4. the subject is noncompliant (does not comply with dosing instructions provided by the Investigator or does not comply with the study visit schedule) and the Investigator determines that withdrawal of the subject is appropriate
5. the subject withdraws consent to participate in the study
6. the site is unable to contact the subject after all reasonable efforts have been exhausted (Lost to Follow-Up)
7. any condition that, in the judgment of the Investigator, would compromise the ability of the subject to comply with the study protocol or complete the study
8. any subject who has to have "rescue" medication will be discontinued

A subject may decide to withdraw from the study at any time, for any reason, without prejudice to subsequent care or treatment by the Investigator.

Subjects who discontinue the study prematurely should be assessed in accordance with the end-of-treatment visit in [Section 6.8](#) and the follow-up procedures in [Section 5.12.1](#).

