### **5.8.4 Compliance and Drug Accountability**

Drug accountability will be recorded at each study visit by count of study drug at each study visit.

A subject will be considered non-compliant with study drug if treatment adherence is less than 80% or more than 120% unless instructed by the Investigator to interrupt dosing for safety reasons ([Section 5.3](#)).

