## 5.12 DISCONTINUATION OF STUDY DRUG AND/OR STUDY PARTICIPATION

1. The Investigator may discontinue study drug and/or study participation in the interest of subject safety. The Investigator must identify specific AEs (laboratory abnormality, intercurrent illness, other medical condition or situation) that result in premature discontinuation of study drug and/or study participation in the eCRF.
2. A subject who withdraws consent to receive study drug may be followed up according to the protocol visit schedule. All attempts must be made to conduct an EOT visit ([Section 6.7](#)).
3. Subjects who meet the following criteria established by Hy's law will be discontinued from the study: alanine aminotransferase or aspartate aminotransferase  $\geq 3$  ULN AND total bilirubin  $> 2$  ULN.
4. Subjects who need "rescue" medication as described in [Section 5.9](#) will be discontinued.
5. Subjects who become pregnant will be discontinued from the study and followed until the pregnancy is concluded.
6. Administration of study drug will be discontinued to all subjects seen by an Investigator who terminates participation in the study prematurely.

Protocol Amendment #3 version: 22 February 2016

*This protocol is solely for the purpose of communicating information about the investigational drug between Insmmed Incorporated and study personnel. Information is not to be reproduced, abstracted or used for sharing of information for any other purpose, whatsoever, except with the written permission of Insmmed Incorporated.*

7. Administration of study drug will be discontinued to all subjects if the study is terminated.

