The Investigator must contact the medical monitor immediately before discontinuing a subject from study drug and/or study participation if possible, or no later than 1 business day after the event. When a subject is prematurely discontinued from study drug, the subject will be given the option to continue in the study, off study drug, until their Month 8 visit (except for subjects enrolled at sites in Japan. All subjects at sites in Japan who discontinue study drug will also discontinue study participation). When a subject is prematurely discontinued from study drug and/or study participation, the Investigator will clearly document the reason in the medical record and complete the appropriate eCRF page describing the reason for discontinuation. If the subject completes all study procedures (including those who discontinued study drug but remain in the study), up to and including the Month 6 study visit, and sputum results indicate non-conversion or relapse/recurrence, they will be invited to participate in a separate open-label study of LAI (Study INS-312), provided all entry criteria have been met for that study. Any subject who discontinues the study prior to the Month 6 study visit will not be eligible to participate in the separate open-label study of LAI (INS-312).

In the event that a subject is withdrawn from the study treatment because of an AE, the subject should be followed and treated by the Investigator until the abnormal parameter or symptom is resolved or stabilized. It is up to the Investigator to determine and document that the AE is either resolved or that it has reached a stable state, after which no further follow-up is necessary.

If a subject fails to complete scheduled assessments in the study, the Investigator must determine the reasons and the circumstances as completely and accurately as possible. "Lost to follow-up" should be marked only in an exceptional case when all documented attempts to reach the subject by the Investigator or other staff members were unsuccessful.

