### 8.4.2.1 Pregnancy

Any pregnancy that occurs during any phase of the study must be reported to Prime Vigilance within 24 hours of learning of the pregnancy using a Clinical Study Pregnancy Form.

The study treatment should be discontinued and the pregnancy should be followed to term. The details of termination must also be reported, including details of birth, the presence or absence of birth defects, congenital abnormalities or maternal and newborn complications, or whether termination was spontaneous or voluntary.

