## **9.5 ANALYSIS POPULATIONS**

### **9.5.1 Intent-to-treat Population**

The intent-to-treat (ITT) population is the set of all randomized subjects.

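### Section 4.3 allows withdrawal from the study, not only from treatment, for noncompliance or a protocol deviation, so ITT outcomes that could be collected are lost

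*Protocol*

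**What the plan says.** **Withdrawal.** Protocol Section 4.3 introduces its list with "A subject may be withdrawn from the study for any of the following reasons". Item 3 is "a major protocol deviation that interferes with the integrity of the study data for this subject". Item 4 applies when "the subject is noncompliant (does not comply with dosing instructions provided by the Investigator or does not comply with the study visit schedule", provided that withdrawal seems appropriate to the Investigator. The synopsis carries the same items. Neither item names LAI, and subjects in both arms take a multi-drug regimen and attend visits. Treatment is open-label (Sections 5.6 and 9.3).

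**Data after leaving the study.** Section 5.12.1 provides an end-of-treatment (EOT) visit followed by telephone contacts. Only the sputum PK subset returns to the clinic, at 28 days and 3 months off LAI.

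**Data after stopping drug.** Section 5.12 treats this differently: "the subject will be given the option to continue in the study, off study drug, until their Month 8 visit". Sites in Japan are excepted. There, stopping study drug also ends participation.

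**Adherence.** Section 5.8.4 says "A subject will be considered non-compliant with study drug if treatment adherence is less than 80% or more than 120" percent, unless the Investigator told the subject to interrupt dosing for safety. It attaches no consequence to that label.

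**Analysis.** Section 9.5.1: "The intent-to-treat (ITT) population is the set of all randomized subjects". A subject whose conversion cannot be evaluated because cultures are missing counts as a non-converter (Section 9.6.1). Missing LAI-arm Month 6 walk distances are imputed from the control distribution (Section 9.6.2). Subjects with major violations are left out of the per-protocol population (Section 9.5.2).

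**The concern.** Items 3 and 4 concern how well treatment or the protocol was followed. Neither makes the subject's sputum or walk distance impossible to measure. Making them grounds for leaving the study turns a conduct problem into lost ITT data. A subject who leaves before three consecutive monthly negative cultures are in hand is scored as a failure whatever later cultures would have shown, and the Month 6 walk is replaced by an imputed value.

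The route is also left to discretion. Outside Japan, a poorly adherent LAI subject may be taken off drug and followed to Month 8 under Section 5.12, or withdrawn from the study under Section 4.3. The protocol does not say which applies, and the person deciding knows the arm. Replacement under Section 4.5 can restore the count of evaluable subjects, but it does not recover outcomes of subjects already randomized.

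**Working it through.** **1. Passages side by side.**

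| Situation | Section | Cultures and walk test to Month 6 |
|---|---|---|
| Off study drug, outside Japan | 5.12 | Can continue, to Month 8 |
| Off study drug, Japan | 5.12 | End, because participation ends |
| Withdrawn for deviation or noncompliance | 4.3, 5.12.1 | End after the EOT visit |
| Primary population | 9.5.1 | Needed for every randomized subject |

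The Section 5.12 option is tied to study drug, which Section 5.8.5 identifies as LAI; Section 5.2 lists no reference study drug. A control subject who is noncompliant with background drugs therefore has no equivalent stated route.

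**2. The plan's figure.** Inputs from Section 9.1: conversion 20% (LAI) and 5% (control), 174 and 87 subjects, two-sided 0.05, continuity-corrected chi-square test. Power is Φ(z), with

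z = (|p₁ − p₂| − c − 1.96·SE₀) / SE₁

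- Pooled rate: (87 × 0.05 + 174 × 0.20)/261 = 0.15
- c = ½(1/87 + 1/174) = 0.00862
- SE₀ = √[0.15 × 0.85 × (1/87 + 1/174)] = 0.0469
- SE₁ = √[0.05 × 0.95/87 + 0.20 × 0.80/174] = 0.0383
- z = (0.15 − 0.00862 − 0.0919)/0.0383 = 1.29, so power is 90.2%

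The stated 261 subjects and at least 90% power are reproduced.

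**3. Illustration of the loss.** The protocol gives no withdrawal rate, so the share w is assumed. Withdrawn subjects are assumed to convert otherwise at their arm's planned rate, and all are counted as non-converters. The LAI rate becomes 0.20 × (1 − w). If w also applies to control, that rate becomes 0.05 × (1 − w).

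| w | LAI rate | Power, N = 261, LAI arm only | Power, N = 261, same w in both arms | Power, N = 351, LAI arm only |
|---|---|---|---|---|
| 0% | 20% | 90.2% | 90.2% | 97.4% |
| 5% | 19% | 86.2% | 87.9% | 95.7% |
| 10% | 18% | 81.1% | 85.3% | 92.9% |
| 20% | 16% | 67.8% | 78.7% | 83.6% |

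The 351 column takes every randomized subject as analysed and lets no other kind of loss lower the rates, so it is favourable to the plan.

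**4. Direction.** Losses in the LAI arm shrink the planned 15-point difference to between 14 points (w = 5%) and 11 points (w = 20%). Losses confined to control would move it the other way, but little: 20% of a 5% rate is 1 point.

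**5. Walk test.** Under control-based imputation the planned 50 m difference becomes about 50 × (1 − w): 47.5, 45 and 40 m for w = 5%, 10% and 20%.

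**The case against.** The case for leaving the text alone has several good parts. Section 4.3 is permissive. Section 5.12 requires contact with the medical monitor before discontinuing a subject where possible, and otherwise within one business day. Sites do not see culture results until after the Month 6 result (Section 3.1), which limits withdrawal driven by the primary outcome. The EOT visit includes sputum and a walk test (Section 6.7), and telephone contacts continue safety and vital-status follow-up. Scoring unevaluable subjects as non-converters, and imputing LAI walk distances from control, both work against LAI when LAI subjects are lost. A subject withdrawn for missing visits may yield few extra cultures under any wording.

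These points reduce the risk without removing it. An EOT visit at withdrawal does not supply the monthly cultures still due, and masked culture results do not prevent decisions influenced by arm or tolerability.

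A reader might infer three stronger things that the documents do not support:

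- *That the rule targets LAI adherence.* Item 4 covers any dosing instruction and missed visits, in both arms. The 80% to 120% threshold exists only for study drug, so more LAI losses are plausible, but it is not tied to withdrawal. Instructed safety interruptions are exempt, and no rate by arm is given.
- *A head count taken from the 90 subjects between 351 and 261.* The 351 is an upper figure. In Section 3.6.1 evaluable means a culture result at baseline and every month to Month 6, so a retained subject with one missed month is among the 90. Any share assigned to items 3 and 4 would be unsourced.
- *That the pregnancy wording shows the same conflict.* Section 5.12 says "Subjects who become pregnant will be discontinued from the study and followed until the pregnancy is concluded"; Section 8.4.2.1 says "The study treatment should be discontinued and the pregnancy should be followed to term" and is silent on participation. The two could usefully be aligned, but they are not a clear contradiction and do not bear on this point.

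**Conclusion.** The point holds as a design weakness and an internal inconsistency. Items 3 and 4 of Section 4.3 permit avoidable loss of ITT outcomes in either arm, contrary to the approach of Section 5.12 and with no analytic gain, since the per-protocol population already deals with major violations. No stated figure is wrong.

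The size is unknown. The fall in power to between 86.2% and 67.8% at 261 subjects rests on two assumptions: that 5% to 20% of the LAI arm is withdrawn for these reasons, and that those subjects would otherwise convert at 20%. If poorly adherent subjects convert less often, or some already have three consecutive negative cultures when they leave, the loss is smaller. If losses are more frequent in the LAI arm, the consequence is a smaller estimated effect and lower power. The documents do not support a claim that the rule would produce a false positive.

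**What to change.** In Section 4.3 and the synopsis, state that items 3 and 4 do not by themselves end outcome collection. Subjects in both arms to whom they apply keep their scheduled sputum, walk-test and adverse-event assessments through Month 6 and Month 8, unless they die, withdraw consent or are lost to follow-up. For adverse events (item 2), add a cross-reference to the Section 5.12 option to continue.

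Leave the existing rules on stopping drug, rescue medication and safety discontinuation as they are; this change concerns only which data are collected. The Japan exception in Section 5.12 and the new follow-up statement must be reconciled. Section 4.3 should also cite Section 6.7, not 6.8, for the EOT visit.

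The cost is protocol wording and some continued visits for poorly adherent subjects. Those visits are already in the schedule of events.
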